10.6 Treatment Groups

The following treatment groups will be assessed:

Group	Description
SC	Standard care (multilayer, multicomponent compression intended for the treatment of VLU)
geko 12h	geko™ version XW, W-3 or variant (12 h daily neuro-stimulation) and SC

10.7 Description of Study Endpoints

10.7.1 Primary Efficacy Endpoint

The primary efficacy endpoint for the study is LHR from TV1 to EOT as compared with LHR from RV1 to TV1. LHRs will be measured by a blinded wound expert using digital images at RV1, TV1, EOT, and at HCV if scheduled.

Each participant will be used as his/her own control, i.e. a participant's healing trajectory before commencement of treatment will be compared to his/her healing trajectory after introduction of treatment.

Since significant non-homogeneity may be expected in VLU participants and their respective healing trajectories, a pre-treatment run-in phase will be used to allow each participant to be used as his/her own control, i.e. a participant's healing trajectory before introduction of treatment will be compared to his/her healing trajectory after introduction of treatment. This allows an intra-group pair-wise comparison to evaluate the efficacy of each treatment regimen.

Additionally, for each participant, it enables generation of a treatment healing rate normalised relative to an initial healing rate. Inter-group (albeit un-paired) comparisons based on this normalised value are likely to be more sensitive than comparison of raw healing rates.

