1.6 Study Rationale, Benefits and Risks

This study is designed to evaluate the efficacy of two geko™ daily treatment durations in conjunction with Standard Care (SC), consisting of multilayer, multicomponent compression therapy intended for the treatment of VLU, compared with each other and to that of SC alone in participants with VLUs. geko™ has been shown to facilitate wound healing in earlier studies (See Section 1.5 Summary of prior clinical studies) and patients receiving the geko™ 6h or 12h daily in addition to SC may experience faster wound healing as well as greater pain reduction than patients treated with SC alone. We believe that treatment with geko™ will in conjunction with SC potentially lead to faster healing and re-epithelialisation than treatment with SC alone for patients with VLU.

A potential risk for participants randomised to the geko™ daily treatments is the possibility of eczema at the application site. This, however, is unlikely based on previous experience with geko™ (20). Potential adverse events for all research participants in this study are intrinsic to the nature of VLUs, including but not limited to: pain and infection at the wound site, and maceration of the surrounding skin.

Not all patients may respond to the geko™ stimulus. Therefore, patients with no involuntary movement of the lower leg/foot at the maximum tolerable device setting will be excluded from the study.

2 Study Objective

The objective of this study is to compare the efficacy of a daily geko™ device treatment durations of 12 hours, in conjunction with SC, to SC alone, in patients with venous leg ulcers.

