During the Run-in Phase participants will be evaluated on a weekly basis. Efficacy evaluations each week will include Investigator assessment of wound healing and measurements of ulcer size using digital images. For the purpose of this study, healing is defined as 100% re-epithelialisation without drainage confirmed at the Healing Confirmation visit (HCV). The compression bandaging system of choice based on local best practice in the study centre in question will be used.

The results of the four-week Run-in Phase during which only SC will be used as treatment, will provide an SC only healing trajectory (LHR curve) (22) for each of the participants and each participant will serve as his/her own control.

At RV1, the Investigator will assess and confirm the patient's eligibility and select the study ulcer. Each participant will have only one VLU selected as the study ulcer. In the situation where a participant has more than one VLU at the RV1 visit, the Investigator will select the largest VLU that meets the eligibility criteria of the protocol as the study ulcer. If other ulcerations are present on the same leg they should be more than 2 cm apart from the study ulcer.

At the first Treatment Phase visit (TV1), once the Investigator has confirmed the participant's continued eligibility, randomisation and assignment to study treatment will take place.

The total maximum study duration is nine weeks, followed up by twelve weeks Follow-up Phase. All participants remaining in the study at the final Treatment Phase visit, TV5, will complete study visits unless they present with 100% re-epithelialisation without drainage as determined by the PI or designee, in which case they will be scheduled for a Healing Confirmation Visit (HCV) in a minimum of 7 days. All participants attending a HCV will complete study visits at this visit regardless if healing is confirmed or not.

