10.2 Sample Size Determination and Rationale

The sample size calculation is based on pilot data pooled from two sources (The Canadian Bandaging Trial (28), and case series) and gives an estimate of effect size (delta/standard deviation) ranging from 0.80 to 1.1. In this design, each group is internally controlled by a four-week baseline, allowing pair-wise intra-group comparison, and normalised inter-group comparison. Assuming the more conservative figure for effect size, and assuming 50% effect size for the reduced dosage group, n=35 per group yields 90% power to establish an effect for geko™ at the lower dosage.

Because of the short study duration, the discontinuation rate is predicted to be about at most 20%. To accommodate the potential discontinuations, the trial proposes to randomise 126 subjects (42 per treatment group).

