10.5.1 Procedure for Interim Analysis

The data to be used in the interim analysis and the treatment assignment of each randomised subject will be given to the statistician. Using this data, the independent statistician will calculate the following metrics for the primary end point:

1. Mean and standard deviation of LHR in each group.
2. The dropout rate at the time of the Interim Analysis, IA
3. The statistical power of the trial at the time of the IA (using a conditional power approach).
 - a. If the statistical power is larger than 50%, then the sample size will be adjusted upward and no Type I error rate adjustment will be made to the final analysis.
 - b. If the statistical power is less than 50%, the Type I error rate will be inflated and statistical adjustment will be made to the final analysis if the decision to increase the sample size is made. That is, the observed p-value, as well as the point estimate of the response rates, and the 95% CIs will be based on:

$$p\text{-value} = 2 * \{1 - T_2(n_1+n_2 - 1) (|z_1 + z_2|/\sqrt{2})\},$$

Healing rate for each treatment group: $\hat{S} = (\sqrt{n_1} \times \hat{S}_1 + \sqrt{n_2} \times \hat{S}_2) / (\sqrt{n_1} + \sqrt{n_2})$,

95% Confidence Intervals = $(\hat{S} - 2 \text{ta}/2:2(n_1+n_2 - 1)\sigma, \hat{S} + 2 \text{ta}/2:2(n_1+n_2 - 1)\sigma)$

where n_1 is the sample size in the treatment group before interim analysis and n_2 is the sample size in treatment group after the interim analysis; $T_2(n_1+n_2 - 1)$ (.) is t distribution with $2(n_1+n_2-1)$ degrees of freedom. The \hat{S}_1 is the healing rate of the n_1 observation before the interim analysis and \hat{S}_2 is the healing rate of the n_2 observation after the interim analysis. The $(\sqrt{n_1} + \sqrt{n_2})\sigma$ is the observed pooled standard deviation before and after the interim analysis.

4. Using the observed metrics above, along with Type I Error Rate of 0.05, the sample size will be re-calculated and the independent statistician will provide the following to the sponsor and the statistician responsible for the trial:
 - a. Re-estimation of sample size using the observed rate of healing and dropout rate
 - b. The difference in percentage of healed subjects
 - c. The healing rate in Treatment arms
 - d. The healing rate in the Control arm
 - e. The power used in calculating the new sample size

No other information will be shared with the sponsor or the statistician responsible for this trial.

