10.5.2 Results of Interim Analysis

The new sample size calculation is:

Based on a pair-wise comparison of geko™ 12h run-in vs treatment:

From the interim data, there is a mean difference of 0.58 mm/week between run-in and treatment and a standard deviation of 0.97 mm/week.

Assuming requirements of 80% power and $p=0.05$ (2-sided) 25 subjects would be needed in the geko™ 12H group. (30)

Little benefit is foreseen in continuing the geko™ 6h group, as statistical significance is not expected at the projected number of subjects in this trial.

From the results of the Interim Analysis the new Treatment Groups are:

Group	Description
SC	Standard care (multilayer, multicomponent compression intended for the treatment of VLU)
geko 12h	geko™ version XW, W-3 or variant (12 h daily neuro-stimulation) and SC

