10.12.1 Efficacy Analyses

Primary Endpoint: The primary efficacy endpoint is linear healing rate (LHR) from TV1 to EOT as compared with LHR from RV1 to TV1. LHRs will be measured by a blinded wound expert using digital images at RV1, TV1, and EOT.

Within treatment groups, treatment phase will be compared to run-in phase by paired non-parametric test (Wilcoxon signed rank). Effects will be compared between groups using non-paired non-parametric tests (Mann-Whitney).

Secondary Endpoints:

Weekly LHR shall be compared as above.

EOT healing status between groups shall be compared by Mann-Whitney U test on the PWAT scores. Weekly LHR can be tested using the same method (and same wording) as final LHR. Incidence of healing shall be compared between groups using Fisher's exact test.

Intra-group pain reduction measured on a visual analogue scale (VAS) will be analysed using paired t-test.

Inter group differences in time to clinically significant reduction in VAS shall be tested using Mann-Whitney u-test.

Intra-group changes to both Quality of Life (QoL) instruments in the study (CWIS and EQ-5D-5L) shall be tested using Wilcoxon signed rank test.

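### Between-arm LHR test: define the effect in mm/week and adjust the Mann-Whitney for run-in LHR, a cheap gain in efficiency rather than a cure for bias

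*Combined protocol and SAP*

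**What the plan says.** Section 2 sets the objective: to "compare the efficacy of a daily geko™ device treatment durations of 12 hours, in conjunction with SC, to SC alone". The between-arm comparison is therefore the one that answers it.

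Section 10.12.1 compares the phases within each arm by Wilcoxon signed rank and then says: "Effects will be compared between groups using non-paired non-parametric tests (Mann-Whitney". No covariate is named. ANCOVA appears in the abbreviation list but in no analysis.

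Section 10.2 describes the run-in as "allowing pair-wise intra-group comparison, and normalised inter-group comparison". Section 10.7.1 says of the run-in that "it enables generation of a treatment healing rate normalised relative to an initial healing rate", and then that "Inter-group (albeit un-paired) comparisons based on this normalised value are likely to be more sensitive than comparison of raw healing rates". No formula or unit is attached to the normalised value.

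The only figures on any scale are in Section 10.5.2: "there is a mean difference of 0.58 mm/week between run-in and treatment and a standard deviation of 0.97 mm/week". Section 3 says the run-in results "will provide an SC only healing trajectory (LHR curve) (22) for each of the participants", and randomisation follows at TV1. Run-in LHR is therefore a pre-randomisation measurement, planned for every randomised participant.

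**The concern.** The run-in exists because healing varies widely between patients, and the plan expects it to sharpen the comparison of arms. Taking a difference uses the run-in with a fixed coefficient of 1. That is the best coefficient only in a special case. When r is low or moderate, it subtracts more run-in noise than it removes patient-to-patient variation, and it can do worse than ignoring the run-in. Regression adjustment estimates the coefficient from the data. At stake is power in the comparison that answers the objective, in a trial of 60 whose sample size is justified only by the within-geko change.

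**Working it through.** **1. The plan's own figure.** Inputs from Section 10.5.2: change 0.58, SD 0.97 mm/week, 80% power, two-sided 0.05.

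- Paired normal formula: (0.97 × (1.960 + 0.842) / 0.58)² = 21.95, so 22.
- Adding z²/2 = 1.92 gives 24. The exact t calculation also gives 24 (power 80.1%, and 81.8% at 25).
- Dividing 23.87 by 0.955, the Wilcoxon efficiency, gives 25.0.

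The stated 25 reproduces as a within-patient difference in mm/week. This supports the difference as the intended scale.

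**2. Variances.** Let s be the SD of LHR in each phase (taken as equal) and r the correlation between phases.

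- Raw treatment rate: s²
- Difference: 2s²(1 − r)
- Linear adjustment for run-in LHR (large samples): s²(1 − r²)

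The difference beats the raw rate only if 2(1 − r) < 1, that is r > 0.5. The adjusted variance divided by the difference variance is (1 + r)/2, which never exceeds 1.

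With unequal SDs, the difference variance minus the adjusted variance is (SD run-in − r × SD treatment)². The gain is therefore nil when r × (SD treatment / SD run-in) = 1.

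**3. Power.** Assumptions not in the documents: the within-geko change of 0.58 is taken as the between-arm difference (no change on SC); change SD 0.97 in both arms; 1:1 allocation with all 60 analysed; equal phase SDs; bivariate normal data; the r values shown. Alpha is two-sided 0.05, as in Section 10.5.2 (Section 10.12 prints 0.05%). With the change SD fixed, s = 0.97/√(2(1 − r)) and the adjusted SD is 0.97 × √((1 + r)/2). Power is simulated for Mann-Whitney tests.

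| r | SD raw | SD adjusted | (1 + r)/2 | Power, raw | Power, difference | Power, residuals |
|---|---|---|---|---|---|---|
| 0.2 | 0.767 | 0.751 | 0.60 | 80% | about 59–60% | 81% |
| 0.5 | 0.970 | 0.840 | 0.75 | 60% | about 59–60% | 72% |
| 0.7 | 1.252 | 0.894 | 0.85 | 41% | about 59–60% | 66% |
| 0.9 | 2.169 | 0.945 | 0.95 | 18% | about 59–60% | 60% |

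Simulated type I error of the residual test was 4.3–5.0%. Under an assumed minimisation scheme (biased coin 0.8, 60 patients), it was 4.6–4.9% when the balancing covariates were unrelated to outcome. It was 2.8–4.0%, which is conservative, when they were prognostic and left out of the model.

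**4. Where the gain changes.**

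- Heavy tails (bivariate t, 4 df): difference 75%; residuals 91/84/80/76% at the same four r.
- r = 0.5 with SD ratio (treatment/run-in) 2, or r = 0.7 with ratio 1.43: the two tests are at 58% and 59%, so no gain.
- r = 0.7 with ratio 0.7: residuals 87%, difference 60%.
- SC also improves by 0.29, leaving 0.58 − 0.29 = 0.29 between arms: difference 19–20%, residuals 30/25/22/20%. The gain is at most about 11 points.
- A patient effect of SD 1 plus independent phase error, a few slopes with inflated error, rescaled to change SD 0.97. With error SD 0.5 and 10% of slopes at 6-fold error (r = 0.47), the tests tie: 92% each at a difference of 0.58. With error SD 0.4 and 5% at 8-fold (r = 0.60), the difference wins 97% to 93% at 0.58 and 74% to 70% at 0.40. With error SD 0.3 and 5% at 10-fold (r = 0.65), it wins 87% to 76% at 0.40.

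**The case against.** The plan nearly closes the definition itself. The endpoint is one phase's rate compared with the other's, Section 10.12.1 speaks of effects straight after the paired comparison, and Section 10.5.2 puts the effect in mm/week. Sections 10.1 and 10.12 defer detail to a separate SAP, which may define it. This stands: the missing formula is missing detail. The covariate-free test, however, is already fixed in the protocol.

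The gain rests on an unstated r. The own-control rationale presumes that patients' trajectories persist from one phase to the next, which implies a substantial r, where the gain is smallest. An LHR fitted to about four points can also be an outlier, and outliers distort the least-squares slope. Both points stand. They limit the expected benefit, and they are the reason to keep the unadjusted difference as a sensitivity analysis.

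Changing a test after an unblinded interim invites a charge of post hoc choice. Section 10.5.1 says: "The data to be used in the interim analysis and the treatment assignment of each randomised subject will be given to the statistician". This bears on the timing and documentation of the change, and does not rule it out.

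A reader might infer that the plan analyses a ratio of treatment to run-in rate, which would break down when the run-in rate is near zero or negative. No section specifies a ratio, and the only figures are differences. A reader might also infer that the between-arm test is biased. It is not: in a randomised comparison, the unadjusted difference is a valid test.

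**Conclusion.** The concern holds as a cheap improvement. Section 10.7.1's claim of greater sensitivity is conditional: with equal phase SDs it needs r above 0.5. Run-in adjustment raises power from about 59–60% to 81/72/66/60% at r = 0.2/0.5/0.7/0.9 under the assumptions in step 3. The documents give neither r, the phase SDs, the allocation ratio nor a between-arm difference, so these figures show direction and range and are not a forecast. The gain is small or nil at high r or when r × (SD treatment / SD run-in) is near 1. It can turn into a loss of about 4–11 points when a few extreme slopes sit on top of a high underlying correlation. Section 10.7.1 describes the normalised comparison and Section 10.12.1 says only effects, so it would be too strong to say that the test is specified on a normalised rate.

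**What to change.** Amend by dated amendment, before any further between-arm LHR data are examined.

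- Section 10.7.1, in place of the normalised-rate paragraph: *The between-group effect is treatment-phase LHR (TV1 to EOT) in mm/week, adjusted for run-in LHR (RV1 to TV1).*
- Section 10.12.1, in place of the Mann-Whitney sentence: *Treatment-phase LHR will be regressed on run-in LHR with arm omitted, and the arms compared by a two-sided Mann-Whitney test on the residuals. This test governs the between-group conclusion. The run-in-adjusted mean difference with 95% CI, from the same model with arm added, is the supporting estimate. An unadjusted Mann-Whitney test on treatment-phase minus run-in LHR in mm/week is a sensitivity analysis.*

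The within-arm signed-rank test is unchanged. If the adjustment is not adopted, one sentence should still define the between-group effect as treatment-phase minus run-in LHR in mm/week.

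Cost: an amendment under Section 13.3 (Lead Investigator and Sponsor signatures, IRB/IEC approval), matching SAP text and one degree of freedom. No new visits or data are needed. The rank test and the adjusted-mean analysis disagreed on significance in 5–7% of simulated trials with normal data and 8–12% with t (4 df) data, so the text must say which governs.

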10.7.2 Secondary Efficacy Endpoints

The secondary efficacy endpoints are:

- Weekly LHR measured by an independent blinded wound expert using digital images taken at each weekly visit until EOT.
- Wound healing status at baseline and EOT assessed by an independent blinded wound expert using PWAT to evaluate digital images taken at RV1, TV1, EOS, and at HCV, if scheduled.
- Incidence of healing at end of study, as determined by the Investigator

"Healing" of the study ulcer is determined by the PI or designee. "Healing" is defined as 100% re-epithelialised without drainage as confirmed at the Healing Confirmation visit (HCV).

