
Secondary Efficacy
 
The overall secondary efficacy endpoints are:
 
 • Weekly LHR of the study ulcer measured by an independent blinded wound expert using digital images taken at each weekly visit until EOT. • Wound healing status at baseline and EOT assessed by an independent blinded wound expert using the Photographic Wound assessment Tool (PWAT) to evaluate digital images taken at RV1, TV1 and EOT and at HCV, if scheduled. • Incidence of healing at EOT, as determined by the by the PI or designee. 
The participant reported secondary efficacy endpoints are:
 
 • Time from TV1 to clinically significant pain reduction measured using a Visual Analogue Scale (VAS) instrument. For the purpose of this protocol a clinically significant reduction of pain is a mean reduction of ≥ 20.65 mm or a mean decrease of $\geq 10-20\%$ in pain as measured on a 0-100 mm VAS. • Time from TV1 to first instance of no study ulcer pain measured using VAS. (No pain = < 5mm on VAS when VAS scores: 0-4 mm = no pain; 5-44 mm = mild pain; 45-74 mm = moderate pain; and 75-100 mm = severe pain) (1). • Pain score at EOT measured using VAS • Change from TV1 in Quality of Life (QoL) at EOT, assessed using the Cardiff Wound Impact Schedule (CWIS) • Change from TV1 in QoL at EOT, assessed using EQ-5D-5L 
 • Wound closure as reported by participants during the Follow-up Phase (FP1-FP3) 	

Safety Assessments
 
Safety will be assessed using the following parameters:
 
 • Incidence of AEs • Incidence of SAEs • Incidence of study ulcer infection • Incidence of study treatment related AEs (including geko™, compression bandaging and any dressings used to treat the study wound) • Incidence of investigational device (geko™) related AEs • Pain in the ulcer site (sudden onset of pain or increase in pain during the study Treatment Phase) 	

Trial Design: This study is designed as a prospective, multicentre, randomised, assessor blinded study designed to compare the efficacy, including participant reported outcomes, of a geko™ treatment in
	

Name of Sponsor/Company: Firstkind Ltd, [name]	
Name of Study Product: geko™ neuromuscular stimulator	

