
Randomisation
 
This is a multi-centre randomised study. Participants will be allocated to treatment groups using Adaptive Covariate Randomisation using an on-line randomisation tool.
 
The randomisation will be applied centrally across the sites.
 
Blinding
 
The independent wound expert measuring the wound area and assessing the healing status of the wound will be blinded to the treatment assignments.
 
The Run-in Phase (RV1 to RV5) is designed to determine each participant's LHR when treated with SC alone. Participants will be seen and evaluated on a weekly basis.
 
The Treatment Phase (TV1 to TV5)
	

Name of Sponsor/Company: Firstkind Ltd, [name]	
Name of Study Product: geko™ neuromuscular stimulator	
Comparator Product: Multilayer, multicomponent compression therapy intended for the treatment of VLU (Standard Care)	
Protocol Number: FSK-VLU- 004	Indication: Venous Leg Ulcers (VLUs)

Participants will be seen and evaluated on a weekly basis. Efficacy evaluations each week will include Investigator assessment of wound healing and measurements of ulcer size using digital photos. Safety evaluations during the Treatment Phase will consist of adverse event assessments at each visit.
 
The Follow-up Phase (FP1-FP3)
 
Participants will be contacted at week 13, week 17 & week 21 to find out when their wound is healed.
	

Healing Confirmation Visit (HCV)
 
Participants whose ulcer presented with 100% re-epithelialisation without drainage as determined by the PI or designee will be scheduled for a Healing Confirmation Visit (HCV) in a minimum of 7 days time after which they will exit the study whether or not healing is confirmed.
 
Duration of Treatment: The duration of the Treatment Phase is four weeks.
 
Total Study Duration: The total study duration is a maximum of nine weeks: four weeks Run-in Phase and four weeks Treatment Phase followed by a HCV in a minimum of 7 days time if applicable. Participants who completed TV5 will have further 12 week Follow-up phase.
	

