4.2.3 Treatment Phase Visits 2- 4 (TV2 – TV4)

Perform the assessments/activities in the following order:

- Administer the study ulcer pain VAS assessment.
- Check for any changes in the participant's health and update the AE or Serious Adverse Events (SAE) CRF pages if applicable.
- Assess concomitant medications.

- Assess compression bandaging (See Section 9.8).
- Assess study ulcer healing (to be performed by treating PI or designee)

If the study ulcer is 100% re-epithelialised without drainage:

- Obtain a digital image of the study ulcer site.
- Provide appropriate follow-up therapy for the healed ulcer and schedule the participant for a Healing Confirmation Visit (HCV) in a minimum of 7 days.
- Administer the CWIS and EQ-5D-5L questionnaires in the participant's primary language.
- Complete the remaining applicable visit procedures.

If the study ulcer is not 100% re-epithelialised without drainage:

- Clean the study ulcer.
- Check for signs of clinical infection. If clinical diagnosis of infection has been made, the participant should be treated with topical antimicrobials or oral antibiotics in accordance with local best practice. SC, or SC plus either gekoTM treatment will continue at Investigator's discretion.
- Obtain a digital image of the study ulcer (if debridement is planned this will be the pre-debridement image). N.B. All study ulcer measurements will be performed using the pre-debridement images.
- Debride the study ulcer to obtain a clean, granulating ulcer base with minimal adherent slough, at the discretion of the Investigator.
- If applicable, obtain a digital image of the study ulcer (post-debridement image)
- Apply appropriate gekoTM to those participants randomised to either gekoTM group.
- Assess for any post-application AEs.
- Schedule the next study visit in one week's time.

Note that TV4 is the final scheduled study product application.

- Apply SC. A non adherent (NA) wound contact dressing and/or an absorbent dressing may be used at Investigator's discretion if required in addition to SC. All dressing use will be recorded.
- Assess and sign the participant diary card (gekoTM groups only).

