4.3 Healing Confirmation

Only those subjects whose study ulcer is 100% re-epithelialised without drainage as determined by the PI or designee during a TV, will be scheduled for a Healing Confirmation Visit (HCV). The HCV is to be scheduled a minimum of 7 days after the first determination of re-epithelialisation.

During the HCV perform the activities in the following order:

- Administer the CWIS and EQ-5D-5L questionnaires in the participant's primary language.

- Administer the study ulcer pain VAS assessment.
- Check for any changes in the participant's health and update the AE or SAE CRF pages if applicable.
- Assess concomitant medications.
- Assess compression bandaging (See Section 9.8).
- Assess study ulcer healing (to be performed by treating PI or designee).

If the study ulcer remains 100% re-epithelialised without drainage:

- Obtain a digital image of the study ulcer site.
- Provide appropriate follow-up therapy for the participant and the healed ulcer and exit the participant from the study.
- Complete the remaining applicable visit (TV5) procedures.

If the study ulcer remains 100% re-epithelialised without drainage at the HCV, the date of healing for the purpose of study results will be the date 100% re-epithelialisation without drainage was first determined by the PI or designee.

If the study ulcer is NOT 100% re-epithelialised without drainage:

- Complete the remaining visit (TV5) procedures.
- Check for signs of clinical infection.
- Clean the study ulcer.
- Obtain a digital image of the study ulcer.
- Provide appropriate follow-up therapy for the participant and the non-healed ulcer and exit the participant from the study.

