10.4 Blinding

The independent wound expert measuring the wound area will receive the wound images without participant identification data or study visit data and he/she will therefore be blinded when measuring the wound area and assessing the healing status of the wound.

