Appendix 2: Photographic Wound Assessment Tool (PWAT)

TABLE I
PHOTOGRAPHIC WOUND ASSESSMENT TOOL

Domain	Assessment	Date Score
1. Edges	0 = Indistinct, diffuse, none clearly visible 1 = Distinct, outline clearly visible, attached, even with wound base 2 = Well-defined, not attached to wound base 3 = Well-defined, not attached to base, rolled under, thickened 4 = Well-defined, fibrotic, scarred or hyperkeratotic	
2. Necrotic Tissue Type	0 = None visible 1 = White/gray nonviable tissue and/or nonadherent yellow slough 2 = Loosely adherent yellow slough 3 = Adherent, soft, black eschar 4 = Firmly adherent, hard, black eschar	
3. Necrotic Tissue Amount	0 = None visible 1 = < 25% of wound bed covered 2 = 25% to 50% of wound covered 3 = > 50% and < 75% of wound covered 4 = 75% to 100% of wound covered	
4. Skin Color Surrounding Wound	0 = Pink or normal for ethnic group 1 = Bright red 2 = White or gray pallor or hypopigmented 3 = Dark red or purple 4 = Black or hyperpigmented	
5. Granulation Tissue	0 = Skin intact or partial-thickness wound 1 = Bright, beefy red; 75% to 100% of wound filled and/or tissue overgrowth 2 = Bright, beefy red; < 75% and > 25% of wound filled 3 = Pink, and/or dull, dusky red and/or fills ≤ 25% of wound 4 = No granulation tissue present	
6. Epithelialization	0 = 100% wound covered, surface intact 1 = 75% to < 100% wound covered and/or epithelial tissue extends > 0.5 cm into wound bed 2 = 50% to < 75% wound covered and/or epithelial tissue extends > 0.5 cm into wound bed 3 = 25% to < 50% wound covered 4 = < 25% wound covered	
TOTAL SCORE		
SIGNATURE		

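### Incidence of healing is called and confirmed by the unblinded treating investigator; a blinded closure reading is already planned and should be added as a confirmatory comparison

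*Combined protocol and SAP*

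**What the plan says.** Section 10.7.2 names the endpoint as "Incidence of healing at end of study, as determined by the Investigator". The Synopsis and section 2.1.2 list the same endpoint at end of treatment (EOT) instead. Healing means full re-epithelialisation without drainage, seen again at an HCV at least 7 days later (sections 4.3 and 9.9.8). Section 4.3 gives the confirmation to the same role as the first call: "Assess study ulcer healing (to be performed by treating PI or designee". Sections 4.2.3 and 4.2.4 assign the first call in the same way.

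At the visits where healing is judged, site staff also carry out this step: "Apply appropriate gekoTM to those participants randomised to either gekoTM group" (section 4.2.3). They sign a diary card that only geko participants have. No sham device is described.

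Blinding is given to one person. The Synopsis says: "The independent wound expert measuring the wound area and assessing the healing status of the wound will be blinded to the treatment assignments". Section 10.4 repeats that this expert is "blinded when measuring the wound area and assessing the healing status of the wound". The expert uses the Photographic Wound Assessment Tool (PWAT), according to the Synopsis "to evaluate digital images taken at RV1, TV1 and EOT and at HCV, if scheduled". The epithelialisation item in Appendix 2 has as its best score "0 = 100% wound covered, surface intact".

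Section 10.12.1 tests PWAT scores between groups by Mann-Whitney and incidence of healing by Fisher's exact test. It does not connect the two.

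**The concern.** No sentence states that the investigator is unblinded. It follows from the treating role, the absence of a sham and the restriction of blinding to the wound expert. A between-arm efficacy comparison therefore rests on a judgement made with knowledge of the arm, although a blinded reading of its main component is already planned.

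Whether the last part of a small ulcer has closed is partly a matter of judgement. If that judgement leans towards closure more often in the geko arm, the Fisher comparison shows a difference that the device did not cause. The HCV guards against a transient error, because the ulcer must look closed twice. It does not guard against a leaning related to the arm, because the same unblinded role makes the second call.

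**Working it through.** **Plan's own figures.** The documents give no power, precision or misclassification rate for incidence of healing. Their current sample size concerns the linear healing rate within the geko arm: a difference of 0.58 and SD of 0.97 mm/week give 25 patients at 80% power (section 10.5.2). An exact paired t calculation gives 80.1% power at n = 24 and 81.8% at n = 25, so that figure is essentially reproduced. It says nothing about healing.

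**Inputs for the illustration.**
- 60 randomised (section 3.1.1). The allocation ratio is not stated, so 30 per arm is assumed.
- Two-sided level 0.05, from section 10.5.2. Section 10.12 prints 0.05%, which conflicts with it; 0.05 is used here.
- True healing rate p, equal in both arms: 10%, 20% and 30%, assumed. For orientation, section 1.3 quotes about 45% healed by 12 weeks. A constant hazard over 4 weeks would give 1 − 0.55^(4/12) = 0.18. This is a rough guide only, because ulcers must still be at least 2 cm² at randomisation, after four weeks of standard care.
- Over-calling d, in percentage points, in the geko arm only and surviving the HCV: assumed.

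**Formula.** With X ~ Bin(30, p) healed on standard care and Y ~ Bin(30, p + d) recorded as healed on geko, sum P(X = x)·P(Y = y) over all pairs with y > x and a two-sided Fisher p-value of at most 0.05.

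**Chance of a false significant result favouring geko:**

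| True healing | d = 0 | d = 5 | d = 10 | d = 20 |
|---|---|---|---|---|
| 10% | 0.5% | 2.9% | 9.5% | 37.2% |
| 20% | 1.1% | 3.6% | 8.8% | 29.8% |
| 30% | 1.3% | 3.5% | 7.7% | 25.9% |

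At p = 18% the corresponding values are 1.0%, 3.5%, 9.0% and 31.0%; 3 points gives 2.3%.

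**A second bias model.** Suppose instead that a fraction f of truly unhealed geko ulcers is called healed. The recorded geko rate is then p + f(1 − p). For p = 10%, 20% and 30%, f = 10% gives 7.8%, 6.3% and 4.8%; f = 20% gives 30.5%, 19.8% and 13.3%. The direction is the same and the size similar.

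**Scale.** With 30 per arm, 5 points is 1.5 ulcers, 10 points is 3 and 20 points is 6. Near the threshold a single call can decide the result: with 5/30 healed on standard care, 12/30 on geko gives p = 0.084 and 13/30 gives p = 0.047.

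**What the blinded reading can check.** PWAT covers closure but has no drainage item. An HCV, and so its image, exists only after the investigator has called closure. The HCV image can therefore expose a false closure call but not a missed one. A missed closure can be seen only on the EOT image.

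**The case against.** This is one of several secondary endpoints, and the wound areas behind the primary endpoint are read blind. Healing needs two examinations at least 7 days apart, so over-calling by 10 to 20 points would mean 3 to 6 of 30 geko ulcers wrongly called closed twice, with no offsetting error on standard care. The over-calling rates are pure assumption, and at 3 to 5 points the effect is small. The blinded reading is not discarded either: PWAT is tested in its own right. Details are left to a separate SAP, which could contain an adjudication rule. All of this stands. It limits the size of the point, but does not remove the gap in the current text.

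A reader might infer that the blinded-confirmed definition should replace the investigator's in the main comparison. The documents do not support that step. Section 10.5.1 has the interim report give the sponsor healing rates by arm, so a new main definition could look data-driven. Investigator-determined healing, and the healing date that depends on it, also run through the Synopsis and sections 2.1.2, 4.3, 5.1, 9.9.8 and 10.7.2. Changing only the analysis section would leave two definitions of healed. Drainage cannot be scored with PWAT, and closures missed by the investigator have no HCV image, so the replacement would remove only part of the bias.

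A reader might also infer that the assessor-blinded label is false. It is not: the plan applies it to the wound expert.

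**Conclusion.** The gap is real and can be closed cheaply. An unblinded role makes both healing calls, and the planned blinded reading of closure is not used to check them. The possible bias favouring geko is a risk, not a demonstrated effect. With 30 per arm, 10–30% true healing and one-sided over-calling (all assumed), false significance favouring geko goes from 0.5–1.3% to about 3–3.6% at 5 points, 8–9.5% at 10 points and 26–37% at 20 points. The documents cannot say which of these applies.

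Two stronger conclusions are not supported. Nothing shows that over-calling will occur, and nothing ranks incidence of healing above the other secondary endpoints. What is supported is an added blinded-confirmed comparison on a secondary endpoint.

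**What to change.** **First reconcile the text.** Section 2.1.2 leaves the HCV out of the PWAT timepoints, while the Synopsis and section 10.7.2 include it. The Synopsis and section 2.1.2 use EOT for the healing endpoint, while section 10.7.2 uses end of study, and EOS for the PWAT images.

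**Then, before database lock, in section 10.12.1 and the SAP:**
1. Keep the pre-specified investigator definition and its Fisher test.
2. Add a second Fisher comparison in which an ulcer counts as healed only if the investigator records closure without drainage and the blinded PWAT epithelialisation score is 0 at both EOT and the HCV. State in advance how a missing or unreadable image is counted.
3. Report agreement between the investigator and the blinded reading, by arm.
4. List EOT images scored 0 where the investigator did not call closure.
5. Make no claim of a between-arm healing difference unless the blinded-confirmed result agrees in direction and approximate size.

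**Cost.** Wording and analysis work on images and readings already planned. No new visits or patients, and no change to the significance level. Unclear or missing images may lower the healed count slightly. Drainage stays with the unblinded investigator, and closures that the investigator misses still have no HCV image.
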